# 3 Study Design

# 3.1 General Design

This is a pilot study that will include a total of 10 subjects with Progressive MS (EDSS 6.5). All subjects will complete 1 month of ES and task-specific training. Expected duration of subject participation is less than 2 months. Baseline assessments will be obtained prior to implantation and post-stimulation assessments will be obtained prior to explantation, with stimulation on and off.

SCREENING	BASELINE	STIMULATION	POST- STIMULATION	
	Baseline Assessments	Minimum 12 Sessions	End Assessments	
Assessment of Inclusion/Exclusion criteria by study team	Clinical, Electromyography, Movement Assessments& Surveys	Stimulation + Task- Specific Training	Clinical, Electromyography, Movement Assessments & Surveys	STUDY END
	No Stim	Percutaneous Stimulation	Stim on/Stim off	
l-month pre- enrollment	Week 0-1	Weeks 1-4	Week 4-5	

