#### 4.1 **Inclusion** Criteria

- Myelopathy secondary to Progressive MS
- No clinical or radiologic MS relapses for > 5 years
- EDSS score of 6.5 (constant bilateral assistance required to walk about 20 meters without resting) as assessed by a Neurologist with a specialty in MS
- Able to ambulate 10 feet independently with or without gait aid use
- At least 21 years of age
- No changes to spasticity medications or dalfampridine over the last 3 months

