*Spasticity:* One or both of the following will be used to measure lower extremity spasticity: the Modified Ashworth Scale (MAS) (Bohannon et al., 1987) where the subject will be placed in a supine position and flexor and extensor muscles are assessed according to the MAS protocol; and the pendulum test which is a biomechanical method of evaluating muscle tone using surface-based kinematic assessments that uses gravity to provoke muscle stretch reflexes during passive swinging of the lower limb.

*Functional mobility test:* The following test will be performed: Timed Up and Go (TUG) (Podsiadlo et al., 1991). The TUG test is used to assess a person's mobility and requires both static and dynamic balance.

*MS QOL Inventory (MSQLI):* Multiple Sclerosis Quality of Life Inventory (Fischer et al., 1999), a comprehensive outcomes assessment battery will be administered to assess many facets of the participants' quality of life. Several scores, are captured, including Overall Health Status, Modified Fatigue Scale, Sexual Satisfaction Scale, Bladder Control Scale, Bowel Control Scale, Perceived Deficits Questionnaire and Mental Health Inventory.

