# 7 Statistical Plan

# 7.1 Sample Size Determination

Due to the pilot phase of this study, no formal power calculations were performed for this proposal. The number of subjects was selected based on budgetary, space, and personnel time constraints. Ten participants (five males; five female) will be enrolled to complete this study, depending on need for contingency subjects. Participants will receive 4 weeks of ES and serve as their own control.

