# 7.2 Statistical Methods

*Statistical Methods:* Continuous data will be summarized as median (inner quartile range). Categorical data will be presented as frequency (percentage). Graphical presentations of subject-level data will be used for all endpoints. Individual data points will be plotted over time, from pre to post stimulation and training.

*Modeling:* Statistical models will be used both to estimate the ES effect on endpoints, as well as to provide estimates of variability to enable sample size estimation for future studies. Models for post-ES treatment will be fit using linear regression using the baseline measure as a covariate. Both the ES treatment effect and the residual variance estimate will be reported. Standard deviations of the differences in pre- and post-ES measurements will also be reported. Furthermore, correlations between pre- and post-ES assessments, as well as post task specific training stim-off and stim-on assessments will be calculated to aid future study design. Transformations of endpoints to achieve symmetry in the distribution (normality will be difficult to assess with this sample size) will be used as necessary.

*Handling of Missing Data:* Due to the small sample size, sophisticated missing data techniques like imputation are likely to be unreliable. For all analyses, only subjects with complete data for the necessary analysis will be included. We will attempt to limit missing data by only enrolling participants who have the physical capacity to complete the training sessions. Only prospective enrollees who have been fully optimized from a rehabilitation point of view will be offered enrollment in the study. To minimize the financial burden on study participants and their families, they will be offered money to offset the cost of travel and accommodation during the study. If a study participant ends the study early, a similar replacement participant will be sought. Missing data in survey instruments will be minimized by allocating time during the study for survey completion, and inspection for completion by study coordinators before moving to the next component of the study.

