# 7.3 Subject Population(s) for Analysis

All-completed population: Only subjects who completed all study related procedures and follow-up will be included; however, the PI may adjust this to include a subject who completed most of the study visits and procedures.

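### A participant who attempts TUG or the gait trials but cannot complete them has no defined value, so the complete-data rule drops them for a reason caused by the outcome

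*Combined protocol and SAP*

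**What the plan says.** Section 7.2 (Handling of Missing Data) judges imputation unreliable at this sample size and states: "For all analyses, only subjects with complete data for the necessary analysis will be included". The same section plans a linear regression of the post value on baseline, the SD of the pre/post differences, pre/post correlations and a stim-off/stim-on correlation. All of these need a number in each state used. The Study Summary also names repeated measures analysis of variance.

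Section 7.3 defines the analysis population: "Only subjects who completed all study related procedures and follow-up will be included". It adds that "the PI may adjust this to include a subject who completed most of the study visits and procedures", without criteria.

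Section 3.1 sets the states. Baseline is without stimulation, and "post-stimulation assessments will be obtained prior to explantation, with stimulation on and off". The tables in 3.2 and 6.4 list gait analysis as primary and TUG as secondary, both measured before and after.

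Section 6.4 says of TUG that the "test is used to assess a person's mobility and requires both static and dynamic balance". For neither TUG nor gait does it give a score, ceiling time, rank or category for a participant who cannot finish. Section 9.3 offers two CRF codes, N/D for a procedure not done and N/A for an item that does not apply. Neither is a value, and neither describes a test that was tried and failed.

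**The concern.** TUG is a time, and gait measures come from completed walking trials. An unfinished attempt yields no number, yet it carries the most information about function. A rule that keeps only complete data removes it, so whether a value is missing depends on how badly the participant did.

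Inability is foreseeable. Entry is at EDSS 6.5, which 4.1 describes as needing constant help on both sides to walk about 20 metres. Section 1.4.2 lists weakness and paralysis below the implant among the risks. Because the post assessment is done in two states, a participant can fail in one and not the other.

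Two distortions follow, in different directions:

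- **Able before, unable after.** The participant leaves the pre/post estimates, which then describe only those who stayed able and look too favourable.
- **Able on, unable off.** The participant leaves any on/off comparison, which then omits the largest on/off contrast.

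Section 7.2 wants these estimates, and their variability, for sizing future studies, so an error would carry forward.

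**Working it through.** **Inputs from the documents.** N = 10, single arm: "Ten participants (five males; five female) will be enrolled to complete this study" (7.1). There is no stated power, alpha or effect to reproduce: "no formal power calculations were performed for this proposal" (7.1). The complete-data rule and the models are in 7.2, the states in 3.1.

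**Assumed inputs.** The documents give no rate of inability. I take 5% to 30% per state, and pre/post correlations of 0.6 and 0.8.

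**1. Which analyses lose the participant.** The rule applies to each analysis separately.

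| State failed | Lost from | Kept in |
|---|---|---|
| Post stim-off only | Baseline/off model, its SD of differences and correlation; on/off correlation | Baseline/on analyses |
| Post stim-on only | Baseline/on analyses; on/off correlation | Baseline/off analyses |
| Both post states | All pre/post and on/off estimates | None |

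Two readings would widen the loss. Read strictly, 7.3 could exclude the participant altogether unless the PI adjusts. A repeated measures ANOVA across all three states, with complete data required, would drop anyone who fails in one.

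**2. How likely a case is.** P(at least one of ten) = 1 − (1 − p)^10.

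| Assumed p | At least one | At least two |
|---|---|---|
| 5% | 40% | 9% |
| 10% | 65% | 26% |
| 20% | 89% | 62% |
| 30% | 97% | 85% |

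**3. Loss of ability after stimulation.** Let k participants become unable and all others improve. Complete cases give (10 − k)/(10 − k) improved. Ranking unable as worst gives (10 − k)/10. The p values are from the exact two-sided sign test.

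| k | Complete cases | Unable ranked worst | Residual df of the baseline-adjusted model (n − 2) |
|---|---|---|---|
| 0 | 10/10, p = 0.002 | 10/10, p = 0.002 | 8 |
| 1 | 9/9, p = 0.004 | 9/10, p = 0.021 | 7 |
| 2 | 8/8, p = 0.008 | 8/10, p = 0.109 | 6 |
| 3 | 7/7, p = 0.016 | 7/10, p = 0.344 | 5 |

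For k = 2: 2 × (1/2)^8 = 2/256 = 0.008, against 2 × (1 + 10 + 45)/1024 = 112/1024 = 0.109.

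**4. Ability only with stimulation on.** Suppose 4 of 10 can do the test only with stimulation on and the other 6 split evenly. Complete cases give 3/6 in favour of on (p = 1.0). Ranking unable as worst gives (3 + 4)/10 = 7/10 (p = 0.344).

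**5. Bias in a mean change when the true change is zero.** I simulated 100,000 trials of ten, with standardised baseline and post values. Participants with the worst 10%, 20% or 30% of post values were unable and dropped.

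| Correlation | Spurious improvement (baseline SDs) at 10%, 20%, 30% |
|---|---|
| 0.6 | 0.08, 0.14, 0.20 |
| 0.8 | 0.04, 0.07, 0.10 |

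The SD of differences fell from 0.633 to 0.624 in the mildest case (1 − 0.624/0.633 = 1.4%) and from 0.895 to 0.849 in the strongest (5.1%). The figure meant for future sizing is therefore understated by about 1% to 5%.

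**The case against.** **The plan never says that inability is missing data.** This is true: 7.2 does not mention inability, and 9.3 reserves N/D for procedures not done. But the planned models need a number, and the documents supply none for a failed attempt. Dropping the participant is what follows if nothing is added.

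**The case does not disappear from the record.** This also stands in part. Section 7.2 requires subject-level plots for all endpoints. Section 8.1 requires new significant findings and worsening of existing conditions to be recorded as adverse events where they qualify. A reader might infer that loss of walking would vanish from the results; the documents do not support that. However, a gap in a plot does not separate inability from a skipped test, and section 8 says expected and non-serious events will not be reported.

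**Entry criteria protect the baseline.** They largely do. A reader might take "Able to ambulate 10 feet independently with or without gait aid use" to be the only walking guarantee, but EDSS 6.5 stands in the same list, and 7.2 limits enrolment to people physically able to complete the training. The gap therefore bites mainly at the post assessment.

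**Being able only with stimulation on is not purely the effect sought.** Correct. Someone able at an unstimulated baseline and unable with stimulation off about four weeks later has also declined. In addition, 7.2 names only a correlation for on versus off, although the Introduction describes the comparison in general terms.

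**Would one or two cases reverse the conclusion?** A reader might infer so from scoring TUG as a rate with zero for unable. Take an assumed baseline of 40 s, with improvers reaching 36 s: each gains 1/36 − 1/40 = 0.00278, or 11.1% of 0.025. With two unable, the mean change is (8 × 0.00278 − 2 × 0.025)/10 = −0.00278, or −11.1%. With one unable it is (9 × 0.00278 − 0.025)/10 = 0, which is not a reversal. With two, the median stays at +11.1%, and 7.2 summarises continuous data by medians. The reversal belongs to that scoring and to means. Assigning zero is also not the transformation to symmetry that 7.2 allows.

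**Conclusion.** The concern holds in this form: a stated complete-data rule, combined with no value for a failed attempt, removes participants from the numeric estimates because of their outcome. Loss of ability flatters the pre/post result, and ability only with stimulation on drops out of on/off comparisons. The loss is analysis by analysis, with plots and adverse event recording as partial safeguards.

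The size cannot be derived from the documents. Under the assumptions shown, two unable participants move a sign test from p = 0.008 to p = 0.109, and outcome-dependent loss of 10% to 30% creates a spurious mean improvement of 0.04 to 0.20 baseline SDs. The trial makes no power claim, so the harm lies in misleading pilot estimates rather than a lost error guarantee. The documents do not support saying that the result reverses, or that the participant vanishes.

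**What to change.** In sections 6.4 and 7.2 and in the CRF, before results are seen:

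1. Record 'attempted, unable' for each test and state, separately from 'not done'.
2. For TUG and overground gait, report the number able at baseline, stim-on and stim-off among all implanted participants who were assessed.
3. For TUG, add a rank-based paired analysis and a median with unable ranked worst. Keep seconds among those able as a companion summary.
4. Apply the complete-data rule only to tests not attempted.
5. For kinematic, kinetic and EMG gait measures, which have no natural worst value, print the able/unable count beside each estimate and state that the estimate is conditional on ability.

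None of this needs imputation, so it respects the plan's objection to it, and treatment and visits do not change. The cost is one more CRF code, a few lines of text and a slightly less familiar TUG summary. The gait estimates remain conditional on ability; the counts disclose that limit but do not remove it.

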# 7.3 Subject Population(s) for Analysis

All-completed population: Only subjects who completed all study related procedures and follow-up will be included; however, the PI may adjust this to include a subject who completed most of the study visits and procedures.

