# 3.3 Primary Safety Endpoints

Primary safety endpoints of the study will be oriented to adverse events that could originate from the implantation of the ES electrodes, or the operation of the neurostimulator device as well as to those that could arise from performing the task-specific training sessions. Participants will be asked to report any discomfort that they encounter throughout the study. A detailed selection of the candidates by the Principal Investigators and the study team will be crucial to select individuals who fit the inclusion criteria of the study, minimizing risk for

34-36

potential adverse events throughout the study. Subjects will undergo a screening phase oriented to identify conditions that could potentially represent a higher than the expected risk for conducting this study.

To visualize electrode positioning of the ES device, X-ray imaging will be performed. To limit adverse events that could result from operating the device, stimulation parameters will be selected within safe ranges as provided by the manufacturer.

#### Subject Selection, Enrollment and Withdrawal 4 Year 1 Year 2 Year 3 Month 1-3 4-6 7-9 10-12 16-18 19-21 13-15 22-24 25-27 28-30 31-33 Subject 1 Screening and baseline visit Subject 2 Stim + task-specific training, Subject 3 post-visit Subject 4 Subject 5 Subject 6 Subject 7 Subject 8 Subject 9 Subject 10

Data Analysis, Interpretation, Documentation

Ten subjects with a diagnosis of Progressive MS (EDSS 6.5) will be enrolled. Subjects will be selected based on the following criteria:

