# 4.4.1 When and How to Withdraw Subjects

Factors that may lead to withdrawal:

- Study subject health concerns
- Protocol violation (e.g., non-compliance)
- Study-related serious adverse events
- Study subject's decision to pursue activities outside of the study protocol, that in the opinion of the PI, may compromise data collected within the study protocol
- The emergence of other problems, events, or information, that may adversely affect the rights, safety, or welfare of the study subject, or may substantially compromise data collected within the study protocol

If a serious adverse event occurs during an activity described in this protocol, a consensual decision will be made between the study subject and the PI regarding withdrawal from the study.

In the event of study withdrawal, the ES electrodes will be explanated. If explanation surgery is urgent due to concern for the subject's health, the cost of the explanation procedure will be covered by the research study. Aside from standard recovery, no adverse effects are anticipated from the removal of percutaneous electrical stimulator.

If a subject fails to attend protocol activities and fails to respond for follow-up, a communication attempt will be made to determine if non-compliance is related to an adverse event.

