#### Procedure to explant ES electrode leads

After completing task-specific training with ES, the adhesive bandage covering the implantation site will be removed, the incision site will be opened, and the leads will be carefully retracted. Finally, the incision site will be cleaned and dressed.

If complications associated with temporary lead implantation (e.g., infection, severe lead migration, device malfunction, etc.) are observed, the PI will make an informed decision whether to perform explantation prior to completion of task-specific training. Participants will be followed up within 5 days of explantation for adverse events. They will be provided information for monitoring the site remotely as well.

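### Completers are the only analysis population and early leavers are replaced, so a participant who leaves because of a complication can drop out of any summary of the primary safety endpoints

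*Combined protocol and SAP*

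**What the plan says.** Section 7.3, which covers the populations for analysis in general, names one population, the all-completed population: "Only subjects who completed all study related procedures and follow-up will be included". It lets the PI add a subject who completed most of the visits and procedures, without giving criteria. Nothing in 7.3 limits this population to efficacy, and no safety, treated or implanted population appears elsewhere.

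Section 7.2 adds two rules. On missing data: "For all analyses, only subjects with complete data for the necessary analysis will be included". On early leavers, whatever their reason: "If a study participant ends the study early, a similar replacement participant will be sought". Section 7.1 plans for this, saying that ten participants "will be enrolled to complete this study, depending on need for contingency subjects".

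Section 3.3 sets the safety endpoints: "Primary safety endpoints of the study will be oriented to adverse events that could originate from the implantation of the ES electrodes". It also covers events from operating the neurostimulator and from the training sessions.

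The protocol expects that some leads may come out early. On explanting the leads, section 5.3 says: "If complications associated with temporary lead implantation (e.g., infection, severe lead migration, device malfunction, etc.) are observed, the PI will make an informed decision". That decision is whether to remove them before training is complete. Section 4.4.1 lists health concerns and study-related serious adverse events among the factors that may lead to withdrawal, and withdrawal itself leads to lead removal.

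**The concern.** The event that section 3.3 is meant to measure can also be the reason a participant fails the test for inclusion in section 7.3. Someone whose participation ends after a complication at implantation, or after an early removal for infection or lead migration, has not completed all procedures. A replacement is then sought, and the set returns to ten people who all finished. A safety summary over that set would be conditioned on the outcome it reports.

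Section 1.4.1 says the study should help show whether temporary stimulation is useful for choosing candidates for a permanent implant. Complications that force leads out within a month bear on that, and with about ten participants each one changes the picture. Section 7.2 calls for categorical data as counts and percentages, but the only population available to supply a denominator is completers.

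**Working it through.** **Which rule excludes the participant.** The complete-data rule in 7.2 works analysis by analysis. Alone, it would keep a removed participant whose adverse event data are complete. The completer rule in 7.3 is what excludes them.

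**Who is excluded.** Section 6.2 sets three training days a week, with a goal of at least 12 sessions. A participant whose leads are removed after two weeks has had about 3 × 2 = 6 of 12 sessions. The week 4 assessment in the section 6.4 table would normally be outstanding, as would the end assessments, which section 3.1 places before explantation with stimulation on and off. Such a person is not a completer and does not clearly qualify as having completed most of the study. A participant with a complication at implantation that ends participation has had no training at all. A removal late in week 4 is different: it may follow the end assessments, or the PI may retain the participant.

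**Inputs.** The planned number is 10 (section 7.1). It was set by budget, space and personnel time, with no power calculation, so there is no stated figure to reproduce. The documents give no removal or complication rate. All counts and risks below are assumptions.

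**Formula.** Exact (Clopper-Pearson) 95% interval for x events in n: lower limit is the 0.025 quantile of Beta(x, n − x + 1), or 0 when x = 0; upper limit is the 0.975 quantile of Beta(x + 1, n − x). For 0/10 the upper limit is 1 − 0.025^(1/10) = 0.308.

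**Removals that end participation, completers against everyone implanted:**

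| Assumed case | Completer set | All implanted |
|---|---|---|
| 1 removed, replaced | 0/10 (0 to 31%) | 1/11 = 9% (0.2 to 41%) |
| 2 removed, replaced | 0/10 (0 to 31%) | 2/12 = 17% (2 to 48%) |
| 3 removed, replaced | 0/10 (0 to 31%) | 3/13 = 23% (5 to 54%) |
| 2 removed, no replacement found | 0/8 (0 to 37%) | 2/10 = 20% (3 to 56%) |
| 2 removed, one retained by the PI, one replaced | 1/10 = 10% (0.3 to 45%) | 2/11 = 18% (2 to 52%) |

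**How often this could arise.** Let p be the risk, per person implanted, of a removal that ends participation, with no other cause of leaving. The chance of at least one before ten people complete is 1 − (1 − p)^10. For p = 5%, 10% and 20% this is 40%, 65% and 89%. The expected number of removals, 10p/(1 − p), is 0.5, 1.1 and 2.5.

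**The case against.** The strongest reply is that no section says adverse events will be tabulated over completers. The modelling and missing-data text in 7.2 concerns before-and-after outcomes, stimulation on/off correlations and surveys. Adverse events have their own section 8. This stands in part: section 7 is silent on how adverse events are tabulated, and 7.3 may have been meant for efficacy alone. But 7.3 does not say so, and it supplies the only population in the plan.

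A second reply is that an early explant is not always a non-completer. Section 5.3 does not equate early removal with withdrawal, a non-urgent removal could follow the end assessments, and 12 sessions is a minimum in section 3.1 but a goal in 6.2. With the PI's discretion added, this stands, and it confines the point to participants who leave early.

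A third is that the zero is built in, because it counts removals among people defined as not removed. That is true. Unplanned removal is also not a named endpoint in 3.3. A reader might infer that the adverse event rate as a whole is forced to zero. The documents do not support that, since completers can have adverse events too.

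A reader might also infer that complications would be lost or go unwatched. The documents say otherwise. Withdrawal reasons (4.4.2), explant dates (5.8.3) and all adverse events (8.2) are recorded. Sections 8.5 and 10.1 provide medical monitoring, the latter by an independent monitor. The legible triggers in 8.4 are a related serious event or the PI's judgment, so no such trigger depends on a percentage.

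Finally, section 1.1 gives the immediate purpose as testing whether these patients respond to stimulation, and complications of an externalised temporary lead may not carry over to a permanent implant. That is fair. The removal rate is relevant to the next step but is not a stated input to it.

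**Conclusion.** The point holds for the summarised safety rate. Followed literally, 7.3 and 7.2 together leave out a participant who ends early because of an implantation, device or training complication, unless the PI chooses to include them. The choice has no criteria and is made in an unblinded study. The bias runs one way, towards fewer complications.

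On the assumed example of two early removals replaced, the reader would see 0/10 in place of 2/12. The intervals overlap widely, so this is not a claim of a statistically distinguishable difference. The objection is that the completer figure for removals that end participation is settled by definition unless the PI adjusts the set. The size rests entirely on assumed counts. The direction rests on reading 7.3 as it is written, to cover every analysis.

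**What to change.** In 7.3, add a safety population of everyone in whom lead implantation was attempted, including those later withdrawn and replaced. Limit the all-completed population to the efficacy summaries.

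In 3.3, state that device-, procedure- and training-related adverse events, and unplanned lead removal with its reason, will be reported as a count and percentage with an exact 95% confidence interval over that safety population.

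The cost is a few sentences and one extra table. The records needed are already required by 4.4.2, 5.8.3 and 8.2, so there are no new visits, data or staff, and the efficacy analyses do not change. The downside is a safety figure that may look less favourable than the completer figure.
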